4.2 INTERVENTION PERIOD PROCEDURES

4.2.1 MID-TREATMENT PROCEDURES

Research staff will meet with client participants virtually to complete the measure battery (UCLA Loneliness Scale, MOS Social Support Survey and Feedback Survey) for the mid-treatment measures at approximately 6-month mark (+/- 4 weeks). Client participants will be compensated \$10 via Visa gift cards or Tango e-gift card for the approximate 30-minute visit. The study coordinator will send the electronic survey to the provider participants for the mid-treatment measures at the 6-month mark (+/- 4 weeks). Provider and/or PSS participants will complete electronic copies of the CPCRN Federally Qualified Health Centers Survey. Provider and/or PSS participants will be paid \$20.00 via Visa gift card or Tango e-gift card for these 40 minutes of their time.

4.2.2 POST-TREATMENT PROCEDURES

Research staff will meet virtually with client participants to complete the finally set of aforementioned measure battery for the post-treatment visit at approximately 12-month timepoint (+/- 4 weeks). Client participants will be compensated \$10 via Visa gift cards or Tango e-gift card for the approximately 30-minute visit. There will be an additional follow-up survey 3-months post-intervention to complete the brief surveys. Clients will additionally be compensated \$10 for this completion of this visit. The study coordinator will send the electronic survey to the provider participants for the post-treatment measures at the 12-month mark (+/- 4 weeks). Provider and/or PSS participants

will complete electronic copies of the CPCRN Federally Qualified Health Centers Survey. After completing the electronic measure, the study coordinator will contact the provider participant to determine if they are willing to participate in the qualitative interview. If they are willing, the study coordinator will meet with them via videoconferencing and lead provider and PSS participants through a semi-structured qualitative interview regarding the Horyzons and various barriers and facilitators to its implementation within their clinic. Provider and PSS participants will be compensated \$20 for completing the post-treatment survey as well as an additional \$30/hr prorated to the nearest half hour if they complete the qualitative interview.

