5. Clients must not have been hospitalized for psychiatric reasons in the three months before enrollment
6. Clients must actively be engaging with medication management via their clinic or another provider
7. Clients must have access to the internet through a phone, tablet, or computer

Exclusion Criteria

1. Clients who do not speak English will not be considered for enrollment
2. Clients with legal guardians (LARs) will not be considered for the study

Provider &/or PSS Participants	Inclusion Criteria
Key Criteria for Inclusion and Exclusion:	
 1. Provider &/or PSS must be 18 years or older 2. Provider &/or PSS must be currently serving clients within their FEP clinic 3. Provider &/or PSS must be able to speak and read English
Number of Subjects	50 client participants with SSDs, 20 provider &/or PSS participants from NC FEP clinics
Study Duration	Each subject's participation will last approximately 12 months from baseline to post-treatment. The entire study is expected to last approximately 24 months (including a 12-month recruitment period).

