3.1 OUTCOMES

Based on previous interviews with providers and peer support specialists, we hypothesize providers and/or PSS will report barriers that may be unique to each clinic as each experiences different outer-, inner, and individual-setting circumstances. Previous barriers, which will likely be reiterated and further described include time constraints, workload, staffing turnover, and perception of the implementation of a new intervention within care. Facilitators are also likely to be distinctive to each clinic, including the support of the team lead in the implementation of Horyzons and time dedicated to Horyzons within care, perception and desire to incorporate evidence-based interventions into clinical treatment to improve client outcomes, and goals and aims of Horyzons aligning with their role.

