4.1.2 BASELINE PROCEDURES

The study coordinator will meet virtually with client participants for approximately 45 minutes to complete all baseline measures. Informed consent and HIPAA authorization will be completed first via DocuSign's electronic consent platform, followed by a demographic and characteristic form collecting basic information about sex, age, ancestry, education (including parent education levels and zip code), cigarette/alcohol use, and basic history of medication/psychosis (including DUP). This will be followed by two psychological measures: the UCLA Loneliness Scale and MOS Social Supports Survey. Once the baseline study measures are complete, the study coordinator will guide clients through a 10-minute orientation to the Horyzons platform, including creating their personal profile and learning the features of the site. Client participants will be paid \$20.00 via Visa gift card for their time and completion of the visit.

The study coordinator will verbally highlight over the phone the study aims, what will be asked of the provider, the timeline of their participation, and that their participation is voluntary for each provider participant at the end of the screening. The provider participants will then be sent the consent forms via DocuSign to sign. In the email and at the top of the consent form in DocuSign there will be a number to call if they have questions. The language will explicitly indicate to call the number prior to consenting and signing the document if they have questions. The provider participants will then be sent the baseline surveys (demographics and CPCRN FQHC Survey) to complete on their own. Providers and PSS will be compensated \$30 for completing the consent and baseline measures.

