5 DATA ANALYTIC PLAN

5.1 PRIMARY OUTCOME MEASURES

1. Qualitative Summaries of Provider and PSS Participant Feedback in Post-Treatment Interview
[Time Frame: up to 12 months]

This qualitative data will be collected post-treatment from providers and PSSs. Individual interviews will discuss the utility and usage of Horyzons within their clinical care in addition to barriers and facilitators on numerous levels (individual, inner setting, and outer setting) of its implementation within their clinic. Feedback from participants will be summarized to include common themes regarding implementation, barriers, and enablers within the clinical setting and ideas for future implementation.

2. Quantitative Summaries of Provider and PSS Participant Experience in Post-Treatment Feedback
[Time Frame: up to 12 months]

This quantitative data will be collected pre-, mid-, and post-intervention from providers and PSSs. Feedback forms will prompt participants to answer questions regarding their experience with barriers and facilitators in implementing an evidence-based practice (in this case Horyzons) in various settings (outer, inner, and individual). The survey will be analyzed regarding changes or lack thereof in the various settings and climate.

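### Section 6.4 lets clinic-affiliated project staff open colleagues' interview transcripts, and providers who leave before month 12 have no stated route to the primary-outcome interview

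*Combined protocol and SAP*

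**What the plan says.** Section 5.1 lists the provider and peer support specialist (PSS) interview as its first primary outcome. On timing: "This qualitative data will be collected post-treatment from providers and PSSs". On format: "Individual interviews will discuss the utility and usage of Horyzons within their clinical care". The synopsis plans "20 provider &/or PSS participants from NC FEP clinics", and its analytic plan has the interviews coded to describe the situation of each clinic.

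**Timing.** The synopsis (Study Phases, Post-treatment) and Section 2.1 (Treatment Period) both have providers asked for the interview at about 12 months, alongside the survey. Section 4.2.2 adds a sequence: "After completing the electronic measure, the study coordinator will contact the provider participant to determine if they are willing to participate". The synopsis entry criterion is "Provider &/or PSS must be currently serving clients within their FEP clinic". Section 3.1 names the barriers it expects to hear about again: "Previous barriers, which will likely be reiterated and further described include time constraints, workload, staffing turnover", among others. The provider survey, the second primary outcome, is repeated: "This quantitative data will be collected pre-, mid-, and post-intervention from providers and PSSs".

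**Access.** Section 6.4 stores all interview transcripts in the project database. It gives direct access to the study coordinators, the project's clinicians and peer specialists, its collaborators and the principal investigator. Section 2.1 describes the peer specialists as study staff who are attached to a participating clinic and who will be interviewed themselves. Section 8 counts peer specialists and providers at the local clinics among the clinical providers involved in the project. Sections 6 and 6.1 use study numbers on research documents, and 6.4 has electronic data de-identified when entered.

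**The concern.** The interviews ask staff what helps and hinders implementation in their own clinic. Section 3.1 expects team-lead support, workload and attitudes to new interventions to come up. Staff may speak less freely on such topics if a co-worker can open the transcript.

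The interview also comes late. A provider who leaves the clinic at, say, month 8 has lived through the turnover that the plan expects, but the plan gives no instruction to interview that person. Because results are to be described clinic by clinic, each clinic's account rests on a handful of speakers. One missing or guarded account therefore matters more than the total of 20 suggests.

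**Working it through.** The plan states no figure to reproduce on this point, and Section 5.4 says that no power calculation was made. The check is mainly a comparison of sections.

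**1. Can a colleague read a transcript?**
- What is in the database: all interview transcripts (6.4).
- Who can open it: among others, project clinicians and peer specialists (6.4).
- Who the peer specialists are: study staff affiliated with a participating clinic, and interviewees (2.1).
- Who the project's clinical providers are: they include local clinic providers (8).
- Safeguards: study numbers (6, 6.1) and de-identification on entry (6.4). No section describes redacting transcripts or restricting same-clinic readers.

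Taken together, the access rule allows a co-worker of the interviewee to read the transcript. It also allows one interviewee to read another's.

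**2. How far do study numbers protect?** 20 providers / 5 clinics = 4 per clinic, assuming an even split. A transcript that describes one clinic and one role among about four speakers may be recognisable to a colleague without a name on it.

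**3. Does an early leaver have a route to the interview?**
- Synopsis, 2.1, 4.2.2 and 5.1: interview at post-treatment, about month 12.
- Synopsis entry criterion: current service in the clinic is required at entry. Nothing removes a provider who leaves later.
- 5.1 time frame: up to 12 months, which permits an earlier interview but does not provide for one.
- No section mentions an interview on departure.

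The leaver stays enrolled and is not barred, but no procedure leads to the interview.

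**4. Must the survey be completed first?** The synopsis and 2.1 have providers asked for both, with no condition. Section 4.2.2 gives only an order of contact. A clarifying phrase there is enough.

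**5. How thin could clinic coverage become?** This is an illustration of non-interview for any cause, refusals included. It does not measure the effect of the missing leaver rule. Let r be the share of providers interviewed. The documents give no such rate, so r is assumed, with four providers per clinic and independent loss.

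P(a clinic has one interview or none) = (1−r)^4 + 4r(1−r)^3. P(at least one of five clinics) = 1 − (1−P)^5.

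| r (assumed) | Expected interviews | P, one clinic | P, any of five |
|---|---|---|---|
| 0.9 | 18 | 0.0037 | 2% |
| 0.8 | 16 | 0.0272 | 13% |
| 0.6 | 12 | 0.1792 | 63% |

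If loss clusters by clinic (beta-binomial, assumed intraclass correlation 0.1), the last column becomes 24% at r = 0.8 and 71% at r = 0.6. In a four-provider clinic, one missed interview is 1/4 = 25% of the possible accounts.

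**The case against.** The strongest reply is that the study calls itself exploratory and that little is actually wrong. Leavers are not excluded, the time frame allows an earlier interview, and remaining staff can describe turnover and workload. The repeated survey starts at baseline ("The provider participants will then be sent the baseline surveys (demographics and CPCRN FQHC Survey) to complete on their own"), so leavers contribute some data. Access is limited to people involved in the project, and data are de-identified on entry. The word for clinicians in 6.4 might mean research clinicians only. The coverage percentages rest on assumed rates and include refusals, which no leaver rule would recover.

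Much of this stands, and it rules out several stronger readings:
- A reader might infer from 4.2.2 that providers who skip the month-12 survey lose the interview. The synopsis and 2.1 do not make the survey a condition.
- A reader might infer that leavers are excluded. The service requirement is an entry criterion only.
- A reader might infer that the themes will understate barriers, or that interviewees will hold back. The documents establish neither, in direction or in size. What interviewees are told about access cannot be judged, because the consent pages are not in the documents.
- A reader might infer from the mention of focus groups in Section 8 that candour is compromised by design. Section 5.1 specifies individual interviews, so the Section 8 wording is an editorial mismatch.

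Two things remain. The narrow reading of the access list does not help with peer specialists, whose clinic affiliation and role as interviewees are stated in 2.1, and Section 8 makes it unsafe for providers. Permission for an early interview is also not a procedure for holding one.

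**Conclusion.** The point holds in two limited parts. (a) As written, 6.4 lets clinic-affiliated project staff, some of them interviewees, read unredacted transcripts of colleagues. The safeguards in the plan are partial with about four interviewees per clinic. Harm to candour is possible, not shown. (b) The first listed primary outcome has no stated route for enrolled providers who leave before about month 12, although the plan expects turnover. Their accounts may be missed, with direction and size not established.

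The firm figures are about four providers per clinic and 25% of a clinic's possible accounts per missed interview, and both assume an even split. The coverage probabilities (2% to 63% under independent loss) depend on assumed interview rates, and neither part relies on them. Both parts concern a primary outcome and are cheap to correct, so the change is worth making. Neither invalidates the design.

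**What to change.** 1. **Section 6.4, access.** Bar staff employed at or affiliated with a participating clinic from unredacted transcripts of interviewees from their own clinic. Bar peer specialists and providers who are interviewees from other interviewees' unredacted transcripts. Give both groups redacted or summarised material instead. Cost: clinic-based project staff cannot code raw transcripts from their own clinic, and staff who are interviewees cannot code raw transcripts at all. A blanket bar on all clinic-employed staff would cost more and is not needed.
2. **Sections 4.2.2 and 5.1, timing.** Offer the same interview at month 12, or on leaving the clinic if that is earlier. Report the numbers enrolled, left, declined and interviewed for each clinic. Cost: leavers will have had shorter exposure to Horyzons and may be harder to reach. The maximum of 20 interviews does not change.
3. **Section 4.2.2, wording.** Add that completing the survey is not a condition for being offered the interview, in line with the synopsis and 2.1.
4. **Section 8, editorial.** Replace the reference to focus groups so that it agrees with the individual interviews in 5.1.

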4.3 Client Procedures

Upon completion of the 12-month intervention period, research staff will collect and amalgamate the passive engagement information of each participant on the platform to assess acceptability and feasibility of Horyzons as part of clinical care. Additionally, client participants' medical records will be examined for service use (e.g., emergency room visits, hospitalizations, outpatient care, etc.) as a result of their mental health.

5 DATA ANALYTIC PLAN

5.1 PRIMARY OUTCOME MEASURES

1. Qualitative Summaries of Provider and PSS Participant Feedback in Post-Treatment Interview
[Time Frame: up to 12 months]

This qualitative data will be collected post-treatment from providers and PSSs. Individual interviews will discuss the utility and usage of Horyzons within their clinical care in addition to barriers and facilitators on numerous levels (individual, inner setting, and outer setting) of its implementation within their clinic. Feedback from participants will be summarized to include common themes regarding implementation, barriers, and enablers within the clinical setting and ideas for future implementation.

2. Quantitative Summaries of Provider and PSS Participant Experience in Post-Treatment Feedback
[Time Frame: up to 12 months]

This quantitative data will be collected pre-, mid-, and post-intervention from providers and PSSs. Feedback forms will prompt participants to answer questions regarding their experience with barriers and facilitators in implementing an evidence-based practice (in this case Horyzons) in various settings (outer, inner, and individual). The survey will be analyzed regarding changes or lack thereof in the various settings and climate.

5.2 SECONDARY OUTCOME MEASURES

1. Mean Change in UCLA Loneliness Scale Score [Time Frame: Baseline, Post-treatment, up to 12 months]

The UCLA Loneliness scale is a 20-item scale. Answers are on a 4-point scale with options "I often feel this way," "I sometimes feel this way," "I rarely feel this way," and "I never feel this way." Possible scores range from 20 to 80. Higher scores reflect worse outcomes (greater feelings of loneliness). The UCLA Loneliness Scale is a part of the PhenX Toolkit.

1. Mean Change in Medical Outcomes Study (MOS) Social Support Survey - total score [Time Frame: Baseline, Post-treatment, up to 12 months]

The MOS Social Support Survey is a 19-item scale. Answers are on a 5-point scale with options "none of the time", "a little of the time", "some of the time", "most of the time", and "all of the time". Possible scores range from 19 to 95. Higher scores reflect higher feelings of social support (more perceived social support). The MOS Social Support Survey is a part of the PhenX Toolkit.

2. Quantitative Summaries of Participant Experience in Post-Treatment Feedback [Time Frame: up to 12 months]

This quantitative data will be collected post-treatment from clients and clinicians. Feedback forms will prompt participants to answer questions regarding their experience with the platform on a scale of 1 to 5, with higher scores reflecting a more positive experience. Frequency counts will be included here.

5.3 TERTIARY OUTCOME MEASURES

1. Change in Engagement with the Horyzons Platform and Attrition over time [Time Frame: up to 12 months]

Changes in engagement with Horyzons will be passively collected for client participants via the platform. Data evaluated will include number of logins, number of journeys, tracks, and activities completed, and number engagements on the community page.

2. Change in use of emergency and social services [Time Frame: Pre- and Post-intervention, up to 12 months]

Collection of use of emergency and social services pre-initiation and post-initiation of Horyzons will be assessed to determine change in use of such services.

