Study Rationale	The purpose of the present study is to investigate the barriers and facilitators to implementing a moderated online social media platform with therapeutic content, Horyzons, as a part of routine care received at first-episode psychosis (FEP) clinics across North Carolina.
Study Objective(s)	
Examine the implementation and integration Horyzons at NC FEP clinics as part of routine clinical care through the following objectives:
 
 1. Identifying the unique barriers and facilitators in implementing Horyzons at each FEP clinic as part of standard care and distinct implementation strategies 2. Evaluate client engagement with Horyzons and attrition as part of clinical care across 12 months 3. Assess change in clients' psychological measures across 12 months and use of emergency and social services across 12 months prior and during engagement with Horyzons platform
Test Article(s) (If Applicable)	Horyzons is a private digital platform that includes curated therapeutic content surrounding issues such as generalized anxiety, social anxiety, social functioning, depression, and distress tolerance. The site also includes a social media function, in which participants and peer support specialists (PSS) can post text, images, and videos. The site is moderated by graduate students and trained fs.
Study Design	This is an open trial enrolling both clients from NC FEP clinics and clinicians and PSSs. FEP clients will participate in the use of Horyzons, a novel digital intervention, which has previously demonstrated benefits to this population and complete psychological measures. FEP clinicians and PSSs will take part in qualitative interviews and surveys to identify unique barriers and enablers in integrating Horyzons as a clinical service within FEP clinics.
Client Participants	
Inclusion Criteria
 
Key Criteria for Inclusion and Exclusion:
 
 1. Clients must be between the ages of 16 and 35 2. Clients must have a diagnosis of schizophrenia, schizoaffective disorder, schizopreniform disorder, or Unspecified Schizophrenia Spectrum or Other Psychotic disorder 3. Clients must be receiving services at one of the five FEP clinics in North Carolina (OASIS, Encompass, Eagle, SHORE, or AEGIS) or one of their stepdown outpatient clinics (STEP and TIDES) 4. Clients must not have had thoughts of harming themselves in the month before enrollment

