2.2.1 INCLUSION CRITERIA

1. Clients must be between the ages of 16 and 35
2. Clients must have a primary diagnosis of schizophrenia, schizoaffective disorder, schizopreniform disorder, or Unspecified Schizophrenia Spectrum or Other Psychotic disorder
3. Clients must be receiving services at one of the five FEP clinics in North Carolina (OASIS, Encompass, Eagle, SHORE, AEGIS) or FEP clinics stepdown care clinics (STEP and TIDES)
4. Clients must not have had thoughts of harming themselves in the month before enrollment
5. Clients must not have been hospitalized for psychiatric reasons in the three months before enrollment
6. Clients must have been actively engaging in psychiatric medication management in the prior month
7. Clients must have access to the internet through a phone, tablet, or computer

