8 RECRUITMENT STRATEGY

Client study subjects will be drawn from the five first episode psychosis clinics in North Carolina (OASIS, Encompass, SHORE, Eagle, and AEGIS). The OASIS clinic was co-developed by [name] for the treatment of people with first episode schizophrenia. Currently, each clinic has a census of approximately 100-150 people and admits approximately 3-5 people per month. Approximately 40 client participants will be recruited from the five clinics, or around 6-8 client participants per clinic. Additionally, all providers have been self-identified as clinicians or PSS providing services to clients at one of the five participating clinics; therefore, we expect approximately 20 providers and/or PSS to participate in this project. As such, we expect that we will be able to recruit the number of participants we would like to involve in this project.

Once a client is referred to the study (or self refers), a study clinician or research assistant will speak with the individual (and any other individuals that she/he indicates, such as a family member) to describe the study protocol, expectations of study participation and potential study risks and benefits. If a client contacts a member of the research project to indicate interest in the study, a member of the research team will explain the study over the phone and use the screening questions to assess potential eligibility. Providers and PSSs will be contacted by phone and/or email in order to obtain consent and schedule focus groups.

Recruitment will be completed by the study coordinator, research assistant, and/or clinical providers involved in this project. The latter includes peer support specialists and providers at the local FEP clinics.

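### The 12-month before-window for service use straddles FEP-clinic entry for recently admitted clients, so the before/during change partly reflects starting FEP care

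*Combined protocol and SAP*

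**What the plan says.** Objective 3 in the synopsis sets out to assess "use of emergency and social services across 12 months prior and during engagement with Horyzons platform". Section 5.3, item 2 lists the outcome as "Change in use of emergency and social services [Time Frame: Pre- and Post-intervention, up to 12 months" and describes it in one sentence: "Collection of use of emergency and social services pre-initiation and post-initiation of Horyzons will be assessed to determine change in use of such services". It gives no denominator, model or rule for person-time.

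Section 4.3 gives the data source: "medical records will be examined for service use (e.g., emergency room visits, hospitalizations, outpatient care, etc". Section 3, item 3 likewise names emergency, inpatient and outpatient services, and says the results will be used to look for possible benefit of engaging with Horyzons.

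The entry criteria in Section 2.2.1 that bear on the look-back are:
- "Clients must be receiving services at one of the five FEP clinics in North Carolina (OASIS, Encompass, Eagle, SHORE, AEGIS", with the step-down clinics also allowed;
- "Clients must have been actively engaging in psychiatric medication management in the prior month";
- "Clients must not have been hospitalized for psychiatric reasons in the three months before enrollment".

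None sets a minimum time in the clinic. The baseline items listed in Sections 2.2 and 4.1.2 include duration of untreated psychosis but not the date of clinic entry. Section 8 reports that "each clinic has a census of approximately 100-150 people and admits approximately 3-5 people per month". The design is an open trial, and no comparison group is described.

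**The concern.** A client who joined the clinic four months before enrolment has eight before-months in which FEP-clinic care could not have occurred, and those months may include the emergency care that led to referral. All of the during-months follow clinic entry. For such a client the contrast spans two changes, starting FEP care and starting Horyzons, and without a comparison group the second cannot be isolated.

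The protocol's own background (Section 1) says that specialty care programs of this kind reduce hospitalization. Part of any before/during change may therefore belong to the clinic, while Section 3 would read it as possible benefit of the platform. If the entry date is not recorded, the two cannot be separated afterwards.

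**Working it through.** The plan states no tenure figure, effect size or power for this outcome, so there is nothing to reproduce. The check uses Section 8's figures: census N = 100–150 per clinic and admissions a = 3–5 per month.

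**1. Share of clients with under 12 months' tenure.** With a stable census and nobody leaving in the first year, s = 12a/N. This gives 36/150 = 24%, 48/125 = 38.4% and 60/100 = 60%. If enrolees resemble the census, that is about 10–24 of the 40 clients in Section 8, or 12–30 of the 50 in Section 2.2.

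**2. Share of before client-months that precede clinic entry.** With entry uniform over the year, these clients average 6 of 12 before-months outside the clinic, so f = s × 6/12.

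**3. Apparent change in FEP-clinic outpatient contacts with no Horyzons effect.** At a constant in-clinic contact rate and none before entry, the during/before ratio is R = 1/(1 − f).

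| Assumption | N=150, a=3 | N=125, a=4 | N=100, a=5 |
|---|---|---|---|
| Base case: f | 0.12 | 0.192 | 0.30 |
| Base case: R | 1.14 | 1.24 | 1.43 |
| No enrolment in first 3 months: f | 0.072 | 0.119 | 0.199 |
| No enrolment in first 3 months: R | 1.08 | 1.14 | 1.25 |
| 30% step-down clients: f | 0.084 | 0.134 | 0.21 |
| 30% step-down clients: R | 1.09 | 1.16 | 1.27 |
| Both restrictions: f | 0.050 | 0.084 | 0.139 |
| Both restrictions: R | 1.05 | 1.09 | 1.16 |
| Exponential stay: f | 0.111 | 0.170 | 0.248 |
| Exponential stay: R | 1.12 | 1.20 | 1.33 |

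- First-three-months row: s = 9a/(N − 3a) = 27/141, 36/113, 45/85, with a mean of 4.5 pre-entry months, so f = s × 4.5/12.
- Step-down row: step-down clients are taken to have over 12 months of care, so f is the base case × 0.7. The combined row multiplies the first-three-months f by 0.7.
- Exponential row: s = 1 − exp(−12a/N) = 0.213, 0.319, 0.451, and f = 1 − s/(12a/N).

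**4. Emergency and inpatient use.** The documents give no pre-entry rate, so the shift cannot be computed. Purely as illustration, suppose the pre-entry rate were k times the in-clinic rate, leaving the hospitalization criterion aside. The apparent change is then 12/[12 + 6s(k − 1)] − 1.
- k = 2: 12/13.44 to 12/15.6, an apparent fall of 11–23%.
- k = 3: 12/14.88 to 12/19.2, an apparent fall of 19–38%.

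**5. Effect of the hospitalization criterion on a window cut at clinic entry.** In the full window, 3/12 = 25% of before-months are free of psychiatric admission by eligibility. If pre-entry months are dropped:
- mean remaining months are 12(1 − s) + 6s = 10.56 at s = 24% and 8.4 at s = 60%;
- mean event-free months are 3(1 − s) + 2.625s = 2.91 and 2.775, where 2.625 is the mean of min(tenure, 3) for tenure uniform on 0–12;
- the event-free share is therefore 2.91/10.56 = 28% and 2.775/8.4 = 33%.

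**The case against.** The strongest reply is that the part that can be sized is peripheral. The outcome is titled emergency and social services; outpatient care appears only among examples in Sections 3 and 4.3. The ratios also set outpatient use before entry to zero, yet Section 4.3 does not limit outpatient care to the FEP clinic, and the synopsis allows medication management by another provider. This stands: the ratios describe FEP-clinic contacts only and do not extend to all outpatient care.

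Enrolees may also not resemble the census. Section 4.1.1 seeks clinically stable clients and step-down clients are eligible, both of which lower the share of recent entrants. This stands too, and is why the range starts at 1.05. Against it, clients admitted during the 12-month recruitment period and enrolled soon afterwards belong to the affected group.

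A reader might infer that the artefact would look like benefit on every service type. The documents do not support that. Nowhere is a rise in outpatient care counted as benefit; Section 3 offers symptom stability as its example. For psychiatric admissions, the three-month criterion removes events from the end of the before-window and so pushes the other way.

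Finally, Section 5.3 says only up to 12 months and gives no denominator, so the comparison is underspecified rather than explicitly wrong, and the study is exploratory. That limits the weight of the point. It does not make the two windows comparable.

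**Conclusion.** The concern holds. With a 12-month look-back, no minimum tenure, no comparison group and no split at clinic entry, the before/during change mixes starting FEP care with any Horyzons effect. Between about 5–14% (restrictive assumptions) and 12–30% (enrolees like the census) of before client-months would precede entry, and the whole range rests on assumed tenure because the documents do not report it. The corresponding ratio of 1.05–1.43 applies to FEP-clinic outpatient contacts alone. The shift in emergency, inpatient and social service use cannot be computed from the documents, and the net direction for psychiatric admissions is uncertain. The point bears on the interpretation of one exploratory tertiary outcome; the primary and secondary outcomes are untouched.

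**What to change.** In Section 5.3, item 2:
- Abstract each client's FEP-clinic entry date during the record review already planned in Section 4.3.
- Report each service type separately, as events per client-month.
- Split the before-window at clinic entry. Show the in-clinic before rate next to the full 12-month rate, with pre-entry months in their own column.
- For psychiatric hospitalization, flag the last three before-months as event-free by eligibility, and do not rely on the in-clinic window alone.
- State that the full-window change will not be attributed to Horyzons.

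The cost is one extra date per client and some SAP wording. The in-clinic before rate is less precise because it rests on fewer months, and its event-free share for psychiatric admissions is larger (step 5 of the working). That is the reason to show both windows rather than replace one with the other.
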